### **3. Analysis**

To evaluate the feasibility and acceptability of the intervention, qualitative analysis will be conducted through interviews with participants and facilitators, in addition, quantitative data will be gathered on mental health symptoms and behavioral outcomes. Qualitative data will be analyzed using ATLAS.ti to explore participant experiences and inform future intervention development. Interview transcripts will be imported into the software for systematic coding. An initial coding framework will be developed both deductively, based on study objectives, and inductively, based on emerging data. Two researchers will independently code a subset of transcripts, refining the codebook through consensus discussions to ensure consistency. All transcripts will then be fully coded, and thematic analysis will be conducted to identify key patterns and relationships. Findings will be used to complement

---

 DSM-5 (PCL-5) in Persian, [Psychometric Properties of the Persian Version of the Posttraumatic Stress Disorder Checklist for DSM-5 \(PCL-5\)](#)

 [WCG Clinical Services: Improving Clinical Trial Quality & Efficiency](#)

quantitative outcomes, providing a deeper understanding of feasibility, acceptability, and potential mechanisms of change within the intervention. To analyse quantitative data, mean differences in subscale scores and total scores between baseline (T1) and follow-up assessments (T2 and T3) will be determined. Linear mixed models will be employed to analyze feasibility and acceptability data, with treatment as a fixed effect, baseline endpoint measurements as covariates, and subjects as a random effect. This approach will allow for the assessment of trends in participant retention, session attendance, and intervention adherence over time while accounting for individual variability.

Feasibility will be assessed through intervention-specific metrics, including recruitment and consent rates, session attendance, assessment completion, protocol adherence, and occurrences of adverse events. Qualitative data collected through Process Evaluation interviews will complement these findings, providing contextual insights and a deeper understanding of the feasibility and acceptability of the program.

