## Abstract

**Background:** A large portion of Afghanistan's population, particularly children, has endured prolonged conflict, poverty, and displacement, leading to significant psychological distress. As children grow into adolescence and adulthood, this distress often manifests in mental health symptoms and an increased likelihood of violent behaviours. With limited mental health professionals and strong stigma around mental health in Afghanistan, culturally adapted, evidence-based interventions are needed.

**Objective:** The study aims to explore the feasibility and acceptability of culturally adapted mental health intervention Problem Management Plus with an additional Emotional Processing module (PM+ EP), in reducing psychological distress in young Afghans. The primary objective is to assess the feasibility of delivering this intervention in Afghanistan and its acceptability by the target communities, and the secondary objective is to assess symptom reduction and behavioural change.

**Methods:** This is a pilot Randomized Control Trial (RCT) with participants aged 16 to 30 in Afghanistan. Eligible participants, young Afghans with high levels of distress and impaired functioning - measured by the Kessler Psychological Distress Scale (K10) -, will be randomized to PM+ EP (n=30) or the waiting group (n=30). The participants will be evaluated through self-report questionnaires at three time points; baseline (T1), four weeks later immediately post-intervention (T2), and 3 months post-intervention (T3), and through a qualitative interview (Process Evaluation) at the end of the study. Outcomes will include measures of anxiety and depression (HSCL-25), aggressive behaviours (AGQ), PTSD symptoms (PCL-5), and daily functioning (WHODAS 2.0).

**Results and Conclusion:** This study will assess the feasibility and acceptability of culturally adapted PM+ EP in Afghanistan and explore the relationship between mental health symptoms and violence among young Afghans. It will be the first to evaluate the feasibility of PM+ EP with this population and could pave the way for a large define RCT examining the effectiveness this approach, should the results show promise.

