### 2.3 Procedure

Participants receiving PM+ EP will meet their facilitator individually, someone of the same gender, and receive the intervention through sessions conducted over Zoom or a similar platform; mitigating the difficulties around accessing psychological support, and the risks associated with safety of participants and stigma around mental health. Participants will receive six individual sessions of PM+ EP over the period of one calendar month.

All participants will complete four surveys for assessment at study points T1, T2 and T3; The Hopkins Symptom Checklist 25 (HSCL-25) to measure for anxiety and depression (Mollica et al, 1987), The Aggression Questionnaire (AQG) to measure violent behaviours (Buss and Perry, 1992), The Post Traumatic Stress Disorder (PTSD) Checklist for DSM-5 (PCL-5) will screen participants for symptoms of PTSD (Weathers et al, 2013), and cognitive ability and overall ability to function will be measured by WHO Disability Assessment Schedule 2.0 (WHODAS 2.0) (WHO, 2012). The latter has been used in studies looking at PTSD and other trauma-symptoms in low-resource settings, to assess the communities' impaired daily functioning (Hamdani et al., 2020). After the final assessment has been complete, a non-random sample of participants will be invited to partake in an interview – the Process Evaluation -, to gather qualitative data to assess the feasibility and acceptability of the program.

The timeline and frequency at which the instruments that will be used for screening, baseline and post intervention are listed in the table below. Some of the listed instruments have translations in Dari or Farsi (Afghan Persian/Iranian Persian). In case there is no translation, the instrument will be translated and back translated by the research team.

*Table 1. Measure Overview and Timeline*

Assessment Timeline					
Enrolment T0	Allocation	Baseline T1	Post-intervention T2	Follow-up - 3 months Post- intervention T3	Close-out
Enrolment:					
Eligibility criteria	X				
Informed consent	X				
Allocation		X			
Intervention:					
PM+ EP		X	X	X	X
Waiting Group					
Assessment:					
K10	X				
HSCL-25		X	X	X	
AGQ		X	X	X	
DSM-5 (PCL-5)		X	X	X	
WHODAS 2.0		X	X	X	
Process Evaluation					X

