### 2.3.3 Outcomes

In this pilot RCT, the primary outcome is to explore the feasibility and acceptability of delivering the PM+ EP intervention in Afghanistan. The study serves to demonstrate whether such interventions could be safely scaled and produce positive outcomes for the target population. The study's secondary outcome is to analyse the relationship between mental health and violence, and to discuss the potential for impact of culturally adapted mental health programming on symptom-change and behavioral change, in particular in reducing violence, and to illustrate the context-specific linkages between mental health and violence. Through this research, we can examine the mental health symptoms, risk factors, and functional impairment, caused by ongoing exposure to conflict or adversity, and advocate for scaling-up adaptation and implementation of evidence-informed mental health interventions in countries such as Afghanistan.

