#### **2.5.6 Fidelity Assessment**

Protocol adherence will be evaluated through two methods. First, helpers will complete a session-by-session checklist after each session, indicating which core components of PM+ EP were delivered. Second, with informed consent, sessions will be audio-recorded, and approximately 10% of these recordings will be analyzed alongside the checklists to assess fidelity.

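### Section 3 ties its only named model to feasibility data, where the treatment effect cannot be estimated for attendance or adherence, and gives the symptom scores only mean differences from T1

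*Protocol*

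**What the plan says.** Section 3 (Analysis) of the protocol deals with the quantitative data in three consecutive sentences.

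- For the questionnaire scores, "mean differences in subscale scores and total scores between baseline (T1) and follow-up assessments (T2 and T3) will be determined". No treatment term or comparison between arms is stated.
- The next sentence reads "Linear mixed models will be employed to analyze feasibility and acceptability data, with treatment as a fixed effect, baseline endpoint measurements as covariates", and adds subject as a random effect.
- The sentence after that gives the model's purpose: "assessment of trends in participant retention, session attendance, and intervention adherence over time".

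This is the only statistical model that the protocol names. The other parts that bear on it are:

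- Section 2.3 (Procedure), on the PM+ EP arm: "Participants will receive six individual sessions of PM+ EP over the period of one calendar month". Section 2.2.2 (Sample Size) offers the waiting group the intervention only once the study is over.
- Section 2.5.6 (Fidelity Assessment): "helpers will complete a session-by-session checklist after each session, indicating which core components of PM+ EP were delivered".
- Section 2.3 (Procedure), on the four questionnaires: "All participants will complete four surveys for assessment at study points T1, T2 and T3".
- The Abstract: "the secondary objective is to assess symptom reduction and behavioural change". Section 2.3.3 (Outcomes) includes in the secondary outcome "to discuss the potential for impact of culturally adapted mental health programming on symptom-change and behavioral change".

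**The concern.** The model's terms do not match the data to which it is assigned. A treatment effect needs the outcome to be observed in both arms, and a baseline covariate needs a value before treatment starts. Session attendance and adherence have neither. Retention is observed in both arms, but it is a yes/no outcome and everyone is present at T1, so its baseline carries no information. The four questionnaire scores have everything the model asks for, and they are not named among its targets.

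Two things are at stake. For two of the three named feasibility variables, an analyst who follows Section 3 cannot produce the treatment effect. And the secondary objective of symptom reduction is left with change from T1. Participants enter because they are distressed (K10 above 15), so change from T1 alone mixes any effect of PM+ EP with natural course and some regression to the mean. The randomised waiting group, measured at the same times, can separate these, but Section 3 states no use of it for the scores. The Abstract makes a larger trial depend on promising results, so a misleading signal would have a consequence.

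**Working it through.** The protocol gives no power, significance level, effect size or SD, so there is no figure of its own to reproduce. The check has two parts.

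**1. Can the treatment effect be estimated?**

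Inputs: 30 per arm (Section 2.2.2); six sessions, PM+ EP arm only during the study (Sections 2.3 and 2.2.2); four scores at T1, T2 and T3 in both arms (Section 2.3). A fixed effect can be estimated separately only if its column in the design matrix is not a linear combination of the others. With every column to be estimated, the rank must equal the number of columns.

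| Outcome | Rows | Fixed-effect columns | Rank |
|---|---|---|---|
| Attendance | 30 × 6 = 180 | intercept, treatment, session | 2 of 3 |
| Attendance | 180 | the same plus a T1 score | 3 of 4 |
| Attendance, no treatment term | 180 | intercept, session | 2 of 2 |
| Retention at T2 and T3 | 60 × 2 = 120 | intercept, treatment, time | 3 of 3 |
| Retention | 120 | the same plus its own (constant) baseline | 3 of 4 |
| Questionnaire score at T2 and T3 | 120 | intercept, treatment, time, treatment-by-time, T1 score | 5 of 5 |

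In the first two rows the treatment column equals the intercept, so treatment is not identifiable. A trend over sessions within the PM+ EP arm is. Checklist adherence has the same structure as attendance. Entering zeros for the waiting group would restore the rank, but the resulting effect would only record that no sessions were offered to that group. The model fits the questionnaire scores without difficulty.

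**2. What does change from T1 alone show?**

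Assumptions, none from the protocol: PM+ EP has no effect; both arms improve by d = 0.2 to 0.5 SD; the T1-T2 correlation ρ is 0.5 to 0.7; 30 participants per arm with no loss; scores are normal with equal SD at both times.

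The SD of change, in units of the score's SD, is √(2(1 − ρ)). The paired t statistic has noncentrality d√30 / √(2(1 − ρ)) on 29 degrees of freedom. For d = 0.2 and ρ = 0.5 this is 0.2 × 5.477 / 1 = 1.095. For d = 0.5 and ρ = 0.7 it is 0.5 × 5.477 / 0.775 = 3.54. The probability that the 95% CI for change in the PM+ EP arm lies wholly on the side of improvement is:

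| d | ρ = 0.5 | ρ = 0.6 | ρ = 0.7 |
|---|---|---|---|
| 0.2 | 0.184 | 0.219 | 0.277 |
| 0.3 | 0.355 | 0.427 | 0.536 |
| 0.5 | 0.754 | 0.841 | 0.927 |

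Under the same assumptions, the T1-adjusted difference between arms excludes zero in about 5% of simulated trials (4.9% to 5.3%; 20,000 trials per setting), as it should.

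**Precision if the model is moved to the scores.** The approximate 95% half-width of the T1-adjusted difference at one time point is 1.96 × √((2/n)(1 − ρ²)). At n = 30 per arm this is 1.96 × √(0.0667 × 0.75) = 0.44 SD for ρ = 0.5 and 1.96 × √(0.0667 × 0.51) = 0.36 SD for ρ = 0.7. At 24 per arm (assumed 20% loss) it is 0.49 and 0.40 SD. These are wide intervals, so the comparison should be called exploratory.

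**The case against.** The strongest reply is that this is a drafting slip in a pilot and that the missing comparison may be in an SAP that is not shown. The reference to baseline endpoint measurements fits only the questionnaire scores, the model sentence directly follows the one on scores, and Section 3 opens by listing symptom data under the evaluation of feasibility. That reading is plausible. But the next sentence names retention, attendance and adherence, so two consecutive sentences assign the model to feasibility data, and an SAP that follows them inherits the problem. This is a stated rule that fails when applied, not a detail left for later.

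Several points stand and limit the finding:

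- The text does not exclude comparing the mean differences between arms. It simply states no such comparison.
- Regression to the mean is probably modest. Selection is on K10 at enrolment (T0), while the outcomes are other instruments with baseline at T1, and the cut-off lies near the scale minimum of 10. Natural course alone supports the argument.
- The 18% to 93% range depends on its assumptions, and the protocol plans no CI or test on within-arm change. The range illustrates the risk; it does not predict this trial's result.
- The secondary aim is worded differently in different places. Section 1 makes it the association between symptoms and violence, and Section 5 leaves effectiveness to further research. The Abstract nevertheless names symptom reduction.
- Adherence in Section 3 may mean adherence by participants rather than delivery by helpers. Either way it exists in one arm only.
- Descriptive feasibility rates are unaffected, and a trend within the PM+ EP arm can be fitted.

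**Conclusion.** The concern holds and should be fixed. For attendance and adherence, two of the model's three named targets, the treatment effect cannot be estimated and no baseline value exists. This follows from the design and needs no assumption beyond the protocol's own statement that the waiting group has no sessions during the study. For retention the model can be fitted but suits the outcome poorly. The four scores that suit it are given only mean differences from T1, so the stated analysis makes no use of the randomised control for symptom reduction. How far that could mislead depends on improvement without treatment: 18% to 93% under the assumed ranges, against about 5% for the comparison between arms. The primary feasibility results remain usable because the descriptive rates in Sections 2.5.2 and 3 do not depend on the model.

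**What to change.** Reword the quantitative paragraph of Section 3.

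- **Questionnaire scores (HSCL-25, AGQ, PCL-5, WHODAS 2.0):** fit the linear mixed model to the T2 and T3 values, with treatment, time, treatment-by-time and T1 score as fixed effects and subject as a random effect. Report the between-arm difference at T2 and at T3 with its 95% CI, labelled exploratory because no power calculation was made.
- **Attendance, PM+ EP arm only:** give the distribution and mean of sessions attended (0 to 6), and the proportion completing all six with an exact or Wilson 95% CI.
- **Adherence, PM+ EP arm only:** summarise the checklist per session; any interval should allow for clustering within participant. If a trend over sessions is wanted, fit it in this arm without a treatment term.
- **Retention and assessment completion at T2 and T3:** give proportions by arm among all randomised, with the between-arm difference and its 95% CI.
- **Engagement frequency and participant feedback:** describe.

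The cost is one paragraph of rewording, with no new data and no change to sample size or visits.

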## 2. Methods

### 2.1 Design and Setting

The study is a stand-alone project, culturally adapting the existing World Health Organization (WHO) PM+ programme and trialling it with a new subject population - Afghan youth. This pilot RCT will be conducted in a community setting in Afghanistan and the research team will be a mix of researchers attached to the Vrije Universiteit (VU) Amsterdam, and field researchers in Afghanistan working with non-profit Peace of Mind Association (PoMA).

This study is a pilot randomized controlled trial (RCT) which involves assessing the feasibility and acceptability of culturally adapted PM+ with an Emotional Processing (EP) module (PM+ EP), and exploring the relationship between mental health symptoms and behavioural change. Self-report assessments will be conducted at three points during the study; prior to delivering the intervention (T1), directly post-intervention (T2), and 3 months-post intervention (T3), and through a qualitative interview conducted at the end of the study.

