#### 2.2.2 Sample Size

Since this is a pilot RCT no power calculations have been carried out. The total sample size will be 60 persons, with half of the participants receiving PM+ EP (N=30) and half assigned to the waiting group (n=30). Randomization will be carried out using a random numbers table generated by computerised software. Those participants in the waiting group will be offered the chance to receive the intervention

post-study. The total number included in the study allows us to evaluate the feasibility and acceptability of the intervention and allow for drop-out rates and incomplete data to be omitted. For the Process Evaluation, a non-random sample size of ten people will be interviewed.

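### The mixed model is said to show trends over time but has no time term; if used on the scale scores, it gives one treatment effect pooled over T2 and T3

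*Protocol*

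**What the plan says.** Three consecutive sentences in Protocol section 3 (Analysis) matter here.

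- On the scale scores: "mean differences in subscale scores and total scores between baseline (T1) and follow-up assessments (T2 and T3) will be determined". No comparison between arms is mentioned.
- On the purpose of the model: "Linear mixed models will be employed to analyze feasibility and acceptability data". The same sentence then sets out its terms: "with treatment as a fixed effect, baseline endpoint measurements as covariates, and subjects as a random effect".
- On what the model delivers: "This approach will allow for the assessment of trends in participant retention, session attendance, and intervention adherence over time", while allowing for variation between individuals.

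Section 2.1 sets three assessments: before the intervention (T1), straight after it (T2) and three months after it (T3). Section 2.3 and Table 1 place HSCL-25, AGQ, PCL-5 and WHODAS 2.0 at all three, in all participants. Section 2.2.2 gives 30 per arm and says the waiting group is offered the intervention after the study.

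**The concern.** The protocol names the terms of the model and then says what those terms will show, and the two do not match. A trend over time needs a term that changes with time. Treatment, the baseline value and the subject effect are each constant within a participant after randomisation.

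There is a second consequence if the model is meant for the scale scores, which the phrase about baseline endpoint measurements suggests. The trial pays for a separate three-month assessment, and the abstract presents the pilot as a possible step to a larger trial. Whoever designs that trial will want to know whether a difference between arms appears early, appears late or fades. The listed model cannot say, and no other between-arm analysis of the scores is stated.

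**Working it through.** The plan gives no computed figure on this point (section 2.2.2 says no power calculation was made), so there is nothing to reproduce. The check is structural, with a simulation for illustration.

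**Inputs from the protocol.** Model terms: section 3. Visits: section 2.1 and Table 1. Sample size of 30 per arm: section 2.2.2.

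**Assumptions, not in the protocol.** Continuous outcome, SD 1, correlation 0.5 between any two visits, a shift of -0.3 from T2 to T3 common to both arms, no dropout.

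**Step 1: the model as listed.** For participant i at visit j (T2 or T3):

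Y_ij = b0 + b1·treatment_i + b2·baseline_i + u_i + e_ij

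Everything on the right except e_ij is the same at both visits. The modelled mean change from T2 to T3 is therefore zero in each arm. The trend is fixed at zero, not estimated. This does not depend on any assumed number.

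**Step 2: what b1 estimates.** With complete data the two visits have equal weight, so b1 estimates (d2 + d3)/2, where d2 and d3 are the true treatment effects at T2 and T3. The last two columns below come from adding visit and treatment-by-visit. Each row is a mean over 300 simulated trials.

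| True (d2, d3) | (d2 + d3)/2 | Listed model | T2, visit terms added | T3, visit terms added |
|---|---|---|---|---|
| (-0.8, -0.2) | -0.5 | -0.485 | -0.778 | -0.192 |
| (-0.5, -0.5) | -0.5 | -0.497 | -0.500 | -0.494 |
| (-0.2, -0.8) | -0.5 | -0.505 | -0.188 | -0.822 |
| (-1.0, 0.0) | -0.5 | -0.486 | -0.974 | 0.002 |

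The listed model cannot tell the four courses apart. The extended model recovers each of them, and estimates the common shift of -0.3 at -0.277 to -0.302.

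**Step 3: do the listed terms fit the named feasibility measures?**

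- Retention: exists in both arms, but has no baseline value and is yes/no at each visit.
- Session attendance: six sessions within one month (section 2.3), so its time scale is session, not T2 and T3. During the study it exists only in the PM+ EP arm, so a treatment effect on it is undefined. It has no baseline value.
- Adherence to the intervention: the same limits as attendance.

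Adding a time term alone would therefore not make the sentence on feasibility trends workable.

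**Step 4: the price in precision of visit-specific estimates.** Under the same assumptions, after adjustment for baseline the residual variance at a visit is 1 - 0.5² = 0.75, and the residual covariance of T2 and T3 is 0.5 - 0.5² = 0.25.

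- Standard error at one visit: √(2 × 0.75/30) = 0.224.
- Pooled over both visits: the variance of the two-visit mean is (0.75 + 0.25)/2 = 0.50, and √(2 × 0.50/30) = 0.183.
- Ratio: 0.224/0.183 = 1.22.

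**Step 5: unequal loss at T3.** With no true effect, a common shift of 0.5 SD and T3 loss of 10% against 40%, the listed model is biased by 0.05 to 0.06 SD. The estimate itself has a standard error of 0.19 to 0.20, so the bias is about a third of one standard error (0.06/0.195 = 0.31). With 15% against 25% loss it is 0.02, and with 20% in both arms it is 0.00. The protocol states none of these inputs.

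**The case against.** The strongest reply is that the protocol assigns this model to feasibility and acceptability data and never says that the scale scores go into it. On that reading, separating T2 from T3 is not something the model was meant to do. The scores already have visit-specific summaries as changes from T1, and the fixed effects for secondary scores are commonly left to a statistical analysis plan.

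Much of this stands. The pooling over T2 and T3 is conditional on the model being used for the scores. A reader might infer that the protocol promises visit-specific treatment effects from the model, or that it has no visit-specific results at all. The documents support neither inference.

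A reader might also infer that the missing visit term makes the treatment estimate seriously biased under unequal dropout. Step 5 does not support that either: the effect is small even at an assumed extreme, and no dropout rate is given.

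Two things remain. First, the deferral argument fails for the trend claim, because the protocol itself lists the terms and states the output that they cannot give. Second, if the model is not for the scores, the protocol states no between-arm analysis of them at all, and the baseline covariate has nothing to refer to.

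**Conclusion.** The sentence on trends is wrong as written. The listed model has no parameter for change over time, whatever the SD, correlation or dropout. Used on the scale scores, it yields one coefficient near the average of the T2 and T3 effects; in the illustration, courses as different as (-1.0, 0.0) and (-0.2, -0.8) both give about -0.5. The sizes rest on assumed values, but the structural conclusion does not.

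The weight is moderate. Feasibility and acceptability are primary and the scores are secondary, so this does not undermine the pilot. It should still be corrected before analysis, because the text as it stands cannot be carried out.

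**What to change.** Replace the model text in section 3 with two statements.

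(a) **Scale scores (HSCL-25, AGQ, PCL-5, WHODAS 2.0).** Fit a linear mixed model with visit (T2, T3), treatment, treatment-by-visit and the baseline score, plus a subject random effect. Report the between-arm difference with a 95% CI at T2 and at T3, labelled as exploratory secondary results. The mean changes from T1 can stay as description.

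(b) **Feasibility measures.** Remove the claim that this model shows trends in retention, attendance and adherence. Report retention and assessment completion by arm and visit, and attendance and adherence by session in the PM+ EP arm only, as proportions with 95% CIs. This fits the list of feasibility metrics at the end of the same section.

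The cost is a short rewrite and a little more analysis, with no new data. Visit-specific intervals are somewhat wider than one pooled interval, by about a fifth under the assumptions in step 4. That is acceptable for a pilot that measures the two time points separately.
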